13.5 Secondary Objectives, Endpoints, Analysis Plans

The secondary endpoints are 1) To assess the impact of ASA and zileuton on three lung cancer gene signatures (an 80-gene bronchial signature, a PI3K pathway gene signature and a nasal diagnostic gene signature) and to compare this to placebo control; (2) To measure urinary PGE-M and LTE(4) levels in current smokers after ASA and zileuton; (3) To assess the safety in current smokers of 12 week exposure to ASA and zileuton; (4) To evaluate a gender effect in the modulatory effects of ASA and zileuton on smoking-related gene expression signature; (5) To explore the effect of ASA and zileuton on the metabolomics profile of the arachidonic acid pathway; and (6) To explore, in a discovery-driven fashion, the effect of ASA and

zileuton on whole-genome gene expression.

For the secondary endpoints, ANOVA will be performed to evaluate whether ASA and zileuton has significantly different impact on changes in the three lung cancer gene signatures and the changes are significantly different from the placebo group. Two sample t tests will be performed to evaluate whether or not there are significant differences in changes in PGE-M, LTE(4) and oxylipin metabolome, respectively, between the treatment and placebo groups. In addition, system biology methods will also be used to analyze the oxylipin metabolome data. Pair-wise comparisons based on two-sample t tests will be performed to whole-genome gene expression data to identify the genes for which ASA and zileuton has a significantly different expression level from the placebo group. Multivariate statistical techniques such as principle component analysis (PCA) will be used to reduce complexity of the whole-genome expression data. PCA analysis will help to identify the major analytes driving a process. For all of the secondary and exploratory analyses, adjustment for multiple comparisons will not be performed. However, the number of comparisons will be reported and we will also cautiously interpret the findings. For both primary and secondary endpoints, if the normality assumption is violated, potential transformation will be sought or nonparametric methods such as Wilcoxon rank sum and Kruskal Wallis tests will be performed.

Descriptive statistics of the type and frequency of all adverse events will be generated, including 95% confidence intervals. For each type of the adverse events, a Fisher's exact test will be performed to compare the frequency of the adverse event between the two groups.

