2.3 Rationale

The combination of ASA and zileuton may be additive or synergistic in inhibiting the arachidonic acid (AA) pathway of inflammatory mediators related to lung carcinogenesis. In an NNK-induced model of lung carcinogenesis, the combination of ASA with the 5-LOX inhibitor A-79175 was more effective than either drug alone, suggesting that concurrent inhibition of both 5-LOX and COX is more effective than inhibition of either pathway alone.²¹ A study of the combination of zileuton and the selective COX-2 inhibitor celecoxib in smokers reported a significant reduction of the levels of PGE-M and LTE(4), suggesting that the combination resulted in inhibition of both LOX and COX pro-inflammatory pathways of AA metabolism.²² The combination of celecoxib to zileuton led to a 62% reduction in PGE-M levels compared to an 18% reduction in PGE-M with zileuton alone; furthermore, the addition of celecoxib to zileuton did not affect the inhibition of LTE(4) by zileuton alone.²²

We propose to evaluate the impact of combined treatment of ASA and zileuton on smoking-related gene-expression signature in nasal epithelium. Additionally, we intend to analyze the persistence of gene expression modulation by ASA in the continuous and intermittent ASA dosing arms by comparing the smoking-related gene expression signature sampled immediately after last dose ASA with that sampled after 10-14 days off ASA and zileuton or double placebo. [name] group has identified a robust smoking-related signature in the bronchial epithelium of smokers in which genes involved in the regulation of oxidant stress, xenobiotic metabolism and oncogenesis are induced and genes involved in regulation of inflammation and tumor suppression are suppressed; this signature has been identified in the nasal epithelium, which appears to be a valid surrogate tissue for bronchial epithelium.^{23, 24} The signature is composed of 119 genes whose expression is altered in both the bronchial and nasal epithelium of current versus never smokers. The first principal component from a principal component analysis across the 119 genes and nasal data from Zhang et al.²⁵ was used to compute a smoking signature score for each of the samples in Zhang et al. and in an independent cohort of 130 nasal samples from current and former smokers. The nasal smoking signature was able to significantly separate never or former smokers from current smokers ($p < 0.01$, see Figure 1).

[figure not shown]

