7.3 Evaluation During Study Intervention

Study participants will return to the clinic for baseline specimen collection (Visit 2). During the visit, weight, blood pressure, pulse, temperature will be measured. A blood sample will be collected for plasma salicylate, ASA, zileuton levels and AA oxylipin analysis. Urine will be collected for PGE-M, LTE(4), and cotinine levels. If urine cotinine level was collected at the screening visit, it will serve as the baseline and will not be repeated at baseline visit. Participants will undergo a baseline nasal epithelium collection via cytology brushing of the nasal turbinate (see Section 7.6) for gene expression analysis. Buccal cells will also be collected (see Section 7.6) and archived as a reserved specimen for gene expression analysis and karyometric analysis. Women of childbearing potential will have urine pregnancy tests prior to receiving study agent at Visits 1 and 2 and also at Visits 3, 4, and 5.

Post baseline specimen collection, participants will be randomized to receive ASA 81 mg daily + Zileuton (Zyflo) 2 x 600 mg BID or placebos for 3 months. Participants will be supplied with a 6-week supply of study agents (to ensure sufficient agent supply until the interim visit), a study agents intake diary and AE diary.

Participants will return for two interim study visits (Visit 3, after 4±1 weeks of agent intervention and Visit 4, after 8±1 weeks of agent intervention). These visits will include vital signs, blood for hepatic panel, check of study agent intake, and a current tobacco use assessment. Concomitant medications and AEs will be

reviewed. Participants will return any unused study agents and receive the next 6-week supply of study agents.

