7.4 Evaluation at Completion of Study Intervention

Participants will take study agents for 12 (\pm 1) weeks and return for the end-of-intervention visit (Visit 5). Participants will take the last dose of the study agents the morning of the end-of-intervention visit. When feasible, this visit will be scheduled between 4-6 hours after the last morning dose of ASA to allow for assessment of plasma ASA concentrations. At this visit, participants will return unused study agents. Evaluations will include vital signs, CBC and CMP panel, check of study agents intake, a current tobacco use assessment, and collection of nasal brushing (for gene expression), urine (for PGE-M, LTE(4), cotinine), blood (for plasma salicylate, ASA, zileuton and AA oxylipin analysis), and buccal cells (for banking and karyometric analysis). Concomitant medications and AEs will be assessed. The study agent diary will be collected.

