7.5 Post-intervention Follow-up Period

Study participants will be instructed to continue to record adverse events and concomitant meds and return for a post-intervention follow-up visit (Visit 6) 10-14 days after the end of intervention visit. The AE and concomitant meds diaries will be collected, AEs will be assessed and study participants will have a hepatic panel done. A collection of nasal brushing (for gene expression), urine (for PGE-M, LTE(4)), blood (for plasma AA oxylipin analysis), and buccal cells (for banking and karyometric analysis) will be done.

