13.2 Randomization/Stratification

Each eligible participant will be randomly assigned to receive ASA + zileuton or placebo based on a random allocation rule. In addition, the randomization will be stratified on gender to assure that equal number of males and females assigned to receive either ASA + zileuton or placebo. No blocking technique will be used.

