13.4 Primary Objective, Endpoint(s), Analysis Plan

The primary endpoint of this study is to compare changes in a smoking-related gene expression signature score in the nasal epithelium of current smokers after ASA and zileuton intervention. We propose to use the smoking gene signature score to assess the impact of ASA and zileuton on smoking-related nasal gene expression. A two-sided two-sample t test will be used to test whether or not there are significant differences in changes in smoking gene signature score (changes from baseline) between the treatment and placebo groups. Based on a sample size of 20 per group, the power will be at least 85% to detect an effect size of ≥ 1 (i.e. \geq one standard deviation difference in the mean changes between the two groups) at a significance level of 5%. Exploratory analyses will be performed to evaluate whether the effect of ASA and zileuton on smoking-related gene expression signature is modulated by gender and whether gene expression changes are associated with ASA and zileuton exposure and changes in PGE-M and LTE(4) levels.

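### Section 13.5 compares changes in PGE-M, LTE(4) and oxylipins without a baseline covariate or a stated scale; a prespecified log-scale ANCOVA would be more precise at almost no cost

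*Combined protocol and SAP*

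**What the plan says.** Section 13.5 gives the comparison between arms as: "Two sample t tests will be performed to evaluate whether or not there are significant differences in changes in PGE-M, LTE(4) and oxylipin metabolome". It does not say whether change means a difference, a percentage or a log ratio. It names neither a covariate nor the post-baseline visit.

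The fallback is: "For both primary and secondary endpoints, if the normality assumption is violated, potential transformation will be sought or nonparametric methods", with rank tests as the examples. No transformation, trigger or order of preference is given.

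Baseline values exist for every marker. Section 7.3 says of Visit 2: "Urine will be collected for PGE-M, LTE(4), and cotinine levels", and has blood drawn at the same visit for oxylipins. The markers are measured again at the end of intervention (section 7.4: "urine (for PGE-M, LTE(4), cotinine), blood (for plasma salicylate, ASA, zileuton and AA oxylipin analysis") and 10–14 days later (section 7.5: "urine (for PGE-M, LTE(4)), blood (for plasma AA oxylipin analysis"). In the summary in section 3, the later collection serves to assess persistence.

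Section 13.2 adds that "the randomization will be stratified on gender". Section 13.4 plans an exploratory analysis of whether "gene expression changes are associated with ASA and zileuton exposure and changes in PGE-M and LTE(4) levels", so it uses the same undefined changes.

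No power is claimed for these markers. The only stated power, at least 85% at 20 per group, belongs to the primary score.

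**The concern.** PGE-M and LTE(4) are the plan's readout of COX and 5-LOX inhibition. If the gene-expression result is null, they help to show whether the drugs reached their targets. About 20 evaluable participants per arm are expected, so precision on these markers is worth having.

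A two-sample t test on change fixes the coefficient of baseline at 1. When the correlation between baseline and follow-up is moderate, that coefficient is too large and the baseline noise is carried into the comparison. ANCOVA estimates the coefficient from data that are collected anyway.

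Scale is the second point. The background describes PGE-M effects as percentages: celecoxib plus zileuton "led to a 62% reduction in PGE-M levels compared to an 18% reduction in PGE-M with zileuton alone". A proportional effect is constant on the log scale but not on the raw scale. If levels are right-skewed, a raw-change test loses power, and the plan settles the scale only after a look at the data.

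**Working it through.** **Inputs from the documents.** 20 evaluable per group, two-sided 5% (section 13.4; stated for the primary test and assumed here for the markers); 1:1 allocation (Schema); PGE-M reductions of 62% and 18% (section 2.3).

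**Assumptions.** Baseline-to-week-12 correlation ρ from 0.3 to 0.9; log-normal levels with log SD σ of 0.5, 0.7 or 0.9; a 40% reduction, chosen between 18% and 62%. The documents give no SD or correlation for these markers.

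**1. The plan's own figure.** Primary score: difference 1 SD, 20 per group, 38 df. Noncentrality = 1/√(2/20) = 3.16; exact power 86.9%. The stated figure of at least 85% is reproduced.

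**2. Variance ratio.** With equal variance σ² at both visits:
- change score: 2σ²(1−ρ)
- ANCOVA residual: σ²(1−ρ²)
- ratio: (1+ρ)/2, times 1 + 1/(40−4) = 37/36 for estimating the slope

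| ρ | 0.3 | 0.5 | 0.7 | 0.8 | 0.9 |
|---|---|---|---|---|---|
| variance ratio | 0.67 | 0.77 | 0.87 | 0.93 | 0.98 |

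At ρ = 0.5, 20 per arm with ANCOVA is worth 20/0.771 ≈ 26 per arm with the change score. The ratio reaches 1 at ρ = 2×36/37 − 1 ≈ 0.95. This step does not need log-normality.

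**3. Power on the log scale, 40% reduction.** The effect is ln 0.6 = −0.511. For ρ = 0.6 and σ = 0.7:
- log-change t: SD = 0.7√0.8 = 0.626; SE = 0.626√0.1 = 0.198; noncentrality 2.58; power 0.71
- ANCOVA: SD = 0.7√0.64 × √(37/36) = 0.568; SE = 0.180; noncentrality 2.84; power 0.79 (37 df)

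Power for σ = 0.5 / 0.7 / 0.9:

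| ρ | log-change t | log ANCOVA |
|---|---|---|
| 0.4 | 0.82 / 0.54 / 0.36 | 0.92 / 0.68 / 0.47 |
| 0.6 | 0.94 / 0.71 / 0.50 | 0.97 / 0.79 / 0.58 |
| 0.8 | 1.00 / 0.95 / 0.79 | 1.00 / 0.96 / 0.82 |
| 0.9 | 1.00 / 1.00 / 0.97 | 1.00 / 1.00 / 0.98 |

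Simulations agree to within simulation error. Allowing for that error, baseline adjustment adds about 9–15 points at ρ 0.4, 3–8 at 0.6, 0–3 at 0.8 and nothing of note at 0.9. Simulated type I error of ANCOVA was about 5%, and adding gender changed power by less than 0.5 point.

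**4. Scale.** Simulated power at ρ = 0.5 for a true ratio of 0.6:

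| log SD | raw-change t | log-change t | log ANCOVA |
|---|---|---|---|
| 0.6 | 52% | 75% | 85% |
| 0.8 | 29% | 50% | 61% |

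The log scale adds 23 and 21 points; baseline adjustment then adds 10 and 11.

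**5. When the model is wrong.** With normal levels, an additive shift, CV 20–30% and ρ 0.4–0.8, log ANCOVA ran from 12 points better (0.68 against 0.56) to 4 points worse (0.85 against 0.89, at CV 30% and ρ 0.8) than the raw-change t test.

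**6. Values below the assay limit.** Put the limit at the 20th percentile of baseline. After a 62% reduction, the share of treated week-12 values below it is Φ(−0.842 − ln 0.38/σ) = 86% / 71% / 59% for σ = 0.5 / 0.7 / 0.9. Replacing these by limit/√2 gave an estimated ratio of 0.48–0.51 against a true 0.38, which is biased toward no effect.

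**The case against.** The case for leaving the plan alone is reasonable. These endpoints are secondary, the oxylipin aim is exploratory, no power is claimed, and section 13.5 promises to report the number of comparisons and interpret with caution. The text is also less open than it first looks. Section 13.4 describes the primary change as change from baseline, so a simple difference is the natural reading. Section 3 ties the follow-up sample to persistence, which makes week 12 the natural effect visit. Section 13.5 already allows a transformation and names it before rank tests. All of this stands. It limits the weight of the point but does not supply a covariate, a scale or a rule.

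The gain also rests on assumptions. A log-normal model favours log methods by construction, and the 62% and 18% come from a celecoxib–zileuton study, not from aspirin. This stands too, and is why ranges are shown.

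Three stronger readings are tempting, and the documents do not support them:
- A reader might infer that the planned tests are biased. They are not: randomization makes the change-score comparison valid.
- A reader might quote a gain of 15–26 points (at ρ 0.6, ANCOVA 0.97 / 0.80 / 0.59 against 0.82 / 0.54 / 0.36). That needs skewed data and a Wilcoxon test on raw change, although the plan lists transformation first.
- A reader might infer a materially inflated false-positive rate from free choice among tests. The plan permits a switch only when normality fails, so picking a test on its result is not what it describes.

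**Conclusion.** The point holds as a gain in precision and clarity, not as an error of validity. Section 13.5 leaves baseline out of the model although it is collected, and leaves the scale to be settled after the data are seen.

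The variance argument is general for equal variances on one scale. How much power it buys depends on ρ, which the documents do not give: it is useful at moderate correlation and negligible near 0.9. The further gain from the log scale depends on right-skewed levels and roughly proportional effects. The documents support that only by describing PGE-M effects as percentages. The lack of multiplicity adjustment is a separate choice, openly declared, and is not part of this point. The primary sample size is not affected.

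**What to change.** In section 13.5:

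- Make the main analysis of PGE-M, LTE(4) and each quantifiable oxylipin an ANCOVA of log week-12 level on arm, log baseline level and gender (the randomization stratum). Report a geometric mean ratio with 95% CI.
- Report week 14 with the same model, as a descriptive estimate of persistence.
- For these markers, replace the open choice between transformation and rank test by one rank test, as sensitivity analysis only.
- If week-12 values fall below the assay limit, use a censored-data (Tobit-type) model or a rank test, with the choice named in advance. Do not substitute limit/√2.

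In section 13.4, use the same log change in PGE-M and LTE(4) for the association with gene expression.

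The cost is SAP wording. Baseline levels and gender are already collected, and no visit, sample or participant is added. The statistical downside is a possible loss of about 4 power points if levels are normal, effects additive and the correlation high.

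### The whole-genome screen in 13.5 is worded as an unadjusted test on expression level, with no visit named and no use of the baseline array, which gives up precision

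*Combined protocol and SAP*

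**What the plan says.** On the gene screen, section 13.5 states: "Pair-wise comparisons based on two-sample t tests will be performed to whole-genome gene expression data". The purpose given is to "identify the genes for which ASA and zileuton has a significantly different expression level from the placebo group". The sentence mentions no visit, baseline value or covariate.

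The other biomarker comparisons with a stated between-arm test are framed differently:

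- Primary score (13.4): "differences in changes in smoking gene signature score (changes from baseline) between the treatment and placebo groups".
- Lung cancer signatures (13.5): "significantly different impact on changes in the three lung cancer gene signatures".
- Urinary and plasma metabolites (13.5): "significant differences in changes in PGE-M, LTE(4) and oxylipin metabolome, respectively, between the treatment and placebo groups".

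The baseline data exist. Section 7.3 says of Visit 2: "Participants will undergo a baseline nasal epithelium collection via cytology brushing of the nasal turbinate". Sections 7.4 and 7.5 add brushings for gene expression at Visit 5 (week 12) and at Visit 6 (10 to 14 days later). On allocation, section 13.2 says "the randomization will be stratified on gender".

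**The concern.** The objective in 1.2 is the effect of the combination on whole-genome expression. With brushings before and after treatment, the natural estimate is the between-arm difference after treatment, made sharper by what is known of each person's starting level. An unadjusted t test on level leaves all stable differences between people (genotype, smoking intensity, gender) in the error term.

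At stake is the sensitivity of the gene list. A gene that the drugs do move may be missed or ranked low because people differ widely in it to begin with. There is also a reproducibility problem: gene expression is sampled at three visits, and the sentence does not say which one supplies the expression level.

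**Working it through.** **Inputs from the documents.** 20 evaluable per group, an effect size of 1 SD and a two-sided 5% level (13.4, stated for the primary test); over about 19,000 genes on the array (9.1); no multiplicity adjustment for secondary or exploratory analyses (13.5).

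**Inputs assumed.** The correlation rho between a gene's Visit 2 and Visit 5 values is not in the documents; 0.3 to 0.8 is shown. Variance is taken as equal at both visits. A per-gene alpha of 0.001 is shown beside 5% to represent a stricter screen; the plan states no such level.

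**The plan's own figure.** Power by noncentral t with n = 20 per group, d = 1, df = 38 and noncentrality d × sqrt(n/2) = sqrt(10) = 3.16 is 86.9% (88.5% by normal approximation). This agrees with the plan's figure of at least 85%. No power is stated for the gene screen.

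**Three analyses of one gene.** Let the true arm difference be 1 SD of the Visit 5 level. The standardized effect is then:

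- level test: d = 1
- change score: d = 1 / sqrt(2(1 − rho))
- baseline-adjusted model: d = 1 / sqrt(1 − rho²)

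For the adjusted model 2 df are deducted (baseline and gender, leaving 36). Any variance explained by gender is not credited.

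| rho | d, change | d, adjusted | 5%: level / change / adjusted | 0.001: level / change / adjusted |
|---|---|---|---|---|
| 0.3 | 0.845 | 1.048 | 86.9 / 74.0 / 89.7% | 36.3 / 21.0 / 41.2% |
| 0.5 | 1.000 | 1.155 | 86.9 / 86.9 / 94.4% | 36.3 / 36.3 / 53.5% |
| 0.7 | 1.291 | 1.400 | 86.9 / 97.8 / 99.1% | 36.3 / 69.2 / 78.9% |
| 0.8 | 1.581 | 1.667 | 86.9 / 99.8 / 99.9% | 36.3 / 91.1 / 94.3% |

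Without the df deduction the adjusted figures rise by less than 1 point. In sample-size terms, adjustment makes 20 per arm behave like 20/(1 − rho²): 22.0 at rho 0.3, 26.7 at 0.5, 39.2 at 0.7 and 55.6 at 0.8.

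**Change score against level.** Var(level)/Var(change) = 1/(2(1 − rho)). Change is therefore more precise only when rho exceeds 0.5, equal at 0.5, and worse below it.

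**False positives.** In 200,000 simulated null genes per rho, with 20 per arm and a 5% test, the level test rejected 4.99%, 4.98% and 4.95% at rho 0.3, 0.5 and 0.8. The change score rejected 4.98%, 5.01% and 4.96%. Neither inflates the error rate. If no gene were affected, about 19,000 × 0.05 = 950 hits would be expected with either variable.

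**The case against.** The strongest reply is that the sentence is loose rather than wrong. Its neighbours in 13.5 compare changes, 13.4 refers to changes in gene expression in an exploratory analysis, and the authors may have meant change here too. That reading is possible, so it cannot be said as fact that the plan compares post-treatment levels or discards the baseline. But the 13.4 remark concerns association with drug exposure and with PGE-M and LTE(4), not the arm comparison, and no section supplies a baseline-adjusted gene screen. If change was meant, the text still has to say so and name the visit.

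A second reply is that the loss is modest at the only level the plan states. At 5% the level test already has 87% power for a 1 SD shift. This stands; the wide gap appears only at the assumed alpha of 0.001, and at rho 0.3 the gain is small at either level. The analysis is also described as discovery-driven, and 13.5 promises cautious interpretation.

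A reader might infer more: that differences between people will be read as drug effects, so that the screen yields extra false genes. The documents do not support this. Allocation is randomized, so chance baseline differences are noise that the 5% error rate already covers. Some chance hits will be genes that differed before treatment, but adjustment changes which null genes are hit, not how many are expected. The expected 950 come from unadjusted testing, a separate matter. Gender is a weak example of chance imbalance, since randomization is stratified on it and 13.3 expects 10 men and 10 women per group to be evaluable.

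**Conclusion.** The point holds as one of precision and specification. As written, the gene screen names neither visit nor baseline, differs from the other between-arm biomarker tests, and leaves removable between-person variation in the error term. For a 1 SD shift in level with 20 per arm, baseline adjustment raises power from 87% to between about 90% and 99.9% at the 5% level, and from 36% to between about 41% and 94% at an assumed alpha of 0.001, over rho 0.3 to 0.8. These gains rest on an assumed rho, equal variances at the two visits and an effect measured in SDs of the level. They do not rest on any claim of bias or of excess false positives.

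Severity is low to moderate: this is an exploratory secondary analysis, and the primary test already uses change from baseline.

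**What to change.** In 13.5, name Visit 5 as the outcome visit for the whole-genome comparison. For each gene, fit a linear model of the Visit 5 value on arm, with the same gene's Visit 2 value and gender (the stratification factor) as covariates, and identify genes by the arm coefficient.

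Do not offer the change score as an unqualified alternative. Below rho 0.5 it is less powerful than the level test (21% against 36% at rho 0.3 and alpha 0.001), and rho will vary between genes. Moderated gene-wise variances are an option, not part of this correction.

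The cost is a change of wording. The primary change score already needs a baseline array for each evaluable participant, so no further samples or assays are required.

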Figure 1. The smoking gene signature score separates never or former smokers from current smokers. The score is significantly different between the two groups in all three analyses by the Wilcoxon rank sum test ($p < 0.01$).

Also of high interest is the effect of ASA and zileuton on three lung cancer gene signatures including an 80-gene signature from bronchial epithelium that distinguishes smokers with and without lung cancer²⁶, an early lung cancer signature derived from bronchial epithelium involving activation of the phosphatidylinositol 3-kinase (PI3K) pathway²⁷; and a nasal gene signature derived from nasal epithelial brushing collected from smokers undergoing bronchoscopy for suspect lung cancer (personal communication). This latter gene signature can distinguish smokers diagnosed with lung cancer vs. those with alternate benign disease of the chest. The signature is enriched among genes that change with lung cancer in the bronchial airway from these same subjects. [name] group is in the process of validating this nasal diagnostic gene expression signature in an independent test set.

Of additional interest is the impact of ASA and zileuton on whole-genome gene expression in nasal epithelium, which would involve a discovery driven approach looking at all genes on the array to discover those impacted by ASA and zileuton intervention.

We also plan to explore the effect of ASA and zileuton on inflammatory mediators derived from multiple AA metabolism pathways. It is recognized that there is complex crosstalk between the three branches of AA metabolism (COX, LOX, and cytochrome P450 (CYP)).²⁸ The inhibition of single or multiple branches may result in the shunting of AA metabolism through other branches. In an LPS-challenged murine model of inflammation, the selective inhibition of the COX pathway using ASA significantly reduced the production of PGE(2) and TXB(2) but also inhibited the CYP and LOX pathways as evidenced by decreased levels of DHETs (CYP pathway metabolites) and 5-HETE and 15-HETE (LOX pathway metabolites). In this model, the selective inhibition of the LOX pathway using the FLAP inhibitor MK 866 reduced the production of 5-HETE and 15-HETE but also reduced PGE(2) and TXB(2); notably, there was a dramatic increase in DHETs, indicating shunting of AA metabolism through the CYP pathway in the face of LOX inhibition.²⁸ In

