9. CORRELATIVE/SPECIAL STUDIES

9.1 Rationale for Methodology Selection

In this proposal we have chosen to measure nasal gene expression using Affymetrix Human Gene 1.0 ST microarrays. The microarray technology is ideal for this proposal because of its cost, ability to estimate gene expression for over ~19,000 genes, previously demonstrated successful use in measuring nasal gene expression.²² and ease of data analysis. The ability to measure additional genes not included in the smoking biomarker is advantageous because it will allow us to look at gene expression alterations associated with ASA and zileuton that are not part of the biomarker. Thus, we have chosen to use microarrays because they are cheaper than next-generation transcriptome sequencing, provide more information than qPCR, and allow us to assess the smoking biomarker in the proposed study using the same platform in which it was developed.

Urinary PGE-M and LTE(4) will be measured by sensitive and specific liquid chromatography-tandem mass spectrometry assays.^{43,29} These assays have been applied to measure urinary PGE-M and LTE(4) levels in smokers.

Urinary cotinine levels will be determined using a commercially available ELISA (GenWay Biotech). This assay kit is a competitive immunoassay designed for the measurement of cotinine in human urine samples.

Plasma concentration of salicylate and ASA will be analyzed by a published high performance liquid chromatography assay.⁴⁴ This assay has been applied to determine the concentration time course of ASA and salicylate following oral administration of 100-500 mg ASA.

A comprehensive panel of AA metabolites will be analyzed by a LC/MS/MS based method developed in [name] laboratory.³³ Currently, about 87 metabolites of arachidonate and linoleate metabolism emanating from COX, LOX, and CYP dependent metabolism can be routinely measured in serum, BALF and urine samples.^{30, 28,34,45}

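### Section 13.5 tests about 19,000 genes and an oxylipin panel with no multiplicity adjustment: at 5% per test about 950 genes would be called significant by chance alone, and the gene contrast is not defined

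*Combined protocol and SAP*

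**What the plan says.** The whole-genome aim is a discovery screen. Section 2.3 describes it as "looking at all genes on the array to discover those impacted by ASA and zileuton intervention", and section 9.1 chooses the microarray partly for its "ability to estimate gene expression for over ~19,000 genes". Section 13.5 gives the method: two-sample t tests to "identify the genes for which ASA and zileuton has a significantly different expression level from the placebo group". It adds principal component analysis to reduce the complexity of the expression data.

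Oxylipins are handled in the same section by two-sample t tests for "significant differences in changes in PGE-M, LTE(4) and oxylipin metabolome, respectively, between the treatment and placebo groups", supplemented by systems biology methods. On the size of the panel, section 9.1 says: "Currently, about 87 metabolites of arachidonate and linoleate metabolism" can be measured routinely. The number to be analysed in this trial is not stated.

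On multiplicity, section 13.5 says "For all of the secondary and exploratory analyses, adjustment for multiple comparisons will not be performed", followed by "However, the number of comparisons will be reported and we will also cautiously interpret the findings". Neither a per-gene significance level nor a false discovery rate appears anywhere. The 5% level is given only for the primary test, in section 13.4.

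**The concern.** The stated purpose is to identify genes, so the product of the analysis is a list. If that list is made of genes with unadjusted p<0.05, an unknown and possibly large part of it is chance, and the plan provides no measure of how large. Reporting the number of tests lets a reader work out the average number of chance hits. It does not show which genes they are.

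There is a second gap. The three signatures, PGE-M, LTE(4) and the oxylipins are compared on changes, but the gene tests are worded as a difference in expression level, with no visit named. The schedule in section 7.1 has nasal brushings at baseline, week 12 and the week-14 follow-up. A reader cannot tell whether the gene tests use week 12 alone, week 14, or change from baseline. A post-treatment comparison in a randomised trial keeps its type I error, so this is an ambiguity and not a bias. It can cost power, and it leaves the contrast open to choice after the data are seen.

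**Working it through.** **Inputs from the documents.** 19,000 genes and up to 87 metabolites (section 9.1); 20 evaluable participants per arm, a two-sided 5% level and an effect of 1 SD (section 13.4, for the primary endpoint).

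**Assumed.** 5% per test for the gene and metabolite tests; the share of genes that truly change; the effect per gene; the baseline correlation; the correlation between genes.

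**The plan's own figure.** Section 13.4 claims at least 85% power. With a noncentral t on 38 df and noncentrality 1 × √(20/2) = 3.16, power is 86.9% (88.5% by the normal approximation). The claim is reproduced. At 0.5 SD the same formula gives 33.8%.

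**Chance hits if the drugs do nothing.** Expected count = number of tests × level.
- Genes: 19,000 × 0.05 = 950. At a 1% level it would be 190, and at 0.1% it would be 19.
- Metabolites: 87 × 0.05 = 4.35, if the panel is as large as the assay allows.

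Correlation between genes leaves the mean alone but widens the spread. In simulations with no drug effect, the 95% range was 891 to 1,013 for independent genes, 821 to 1,087 for blocks of 100 genes with r = 0.3, and 553 to 1,674 for 10 large modules with r = 0.3. The documents support no particular structure. The point is that the total number of hits may not by itself show whether there is any signal.

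**False share of the declared genes.** With s the share that truly changes, false share = (1−s)×0.05 / [(1−s)×0.05 + s×power]. For s = 1% at 1 SD: false calls 18,810 × 0.05 = 940.5; true calls 190 × 0.869 = 165.1; false share 940.5/1,105.6 = 85%.

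| Genes truly changed | False share, 1 SD | False share, 0.5 SD |
|---|---|---|
| 1% | 85% | 94% |
| 5% | 52% | 74% |
| 10% | 34% | 57% |
| 20% | 19% | 37% |

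Half the list is false when s = 0.05/(0.05 + power): 5.4% of genes at 1 SD and 12.9% at 0.5 SD. Below those shares, most declared genes are false.

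**Effect of false discovery rate control.** With no drug effect, Benjamini-Hochberg at 5% declared on average 0.09 genes (independent) or 0.015 (blocks of 100), instead of about 950. With 1% of genes changed by 1 SD, independent genes:

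| Rule | True genes kept | False genes kept |
|---|---|---|
| p<0.05 | 165 | about 940 |
| q<0.10 | 41 | 5 |
| q<0.05 | 24 | 1 |

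Repeat simulations put the 24 between 21 and 26. Bonferroni would need p<2.6×10⁻⁶, with about 2.5% power per gene at 1 SD, which is too strict for a discovery aim.

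**Use of baseline.** Relative to the variance of the post-treatment value, and with baseline correlation rho, the change score has variance 2(1−rho) and ANCOVA has 1−rho² (37 df). Here 1 SD means one SD of the post-treatment level. Section 13.4 defines its 1 SD on the change, so the change-score row does not contradict that section.

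| Power at 1 SD | rho 0.3 | rho 0.5 | rho 0.7 |
|---|---|---|---|
| Post-treatment only | 87% | 87% | 87% |
| Change from baseline | 74% | 87% | 98% |
| ANCOVA | 90% | 94% | 99% |

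**The case against.** The best defence is that this is a disclosed choice with limited reach. The objectives and section 13.5 label both analyses exploratory, the lack of adjustment is stated openly, the number of comparisons will be reported, and caution is promised. The primary endpoint is a single test and is not touched, and no efficacy decision in the documents rests on the gene list. All of that stands, and it is why this is an improvement to make and not a threat to the trial's main result. It does not close the gap: caution sets no criterion, and principal components and systems biology methods do not control error gene by gene.

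It is also fair that 950 depends on a 5% level the plan never states for these tests. The absence of any level is part of the same problem, because the length of the list is then settled after the data are seen.

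The metabolite part is weaker. The figure of 87 covers arachidonate and linoleate metabolites and is the assay's capacity, whereas this trial profiles arachidonic acid oxylipins in plasma, so 87 is probably an upper bound. A complete absence of effect is also unlikely for drugs that act on these pathways. The case for q-values there is consistency at no cost more than a large expected error.

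Finally, ANCOVA would differ from the change-score t tests planned for the other endpoints. What is essential is to name the visit and the contrast. ANCOVA is recommended because 1−rho² never exceeds 1 or 2(1−rho); the price is one degree of freedom.

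**Conclusion.** The concern holds. Under an assumed 5% per test, about 950 of 19,000 genes would be declared significant with no drug effect, plus about 4 metabolites if the panel has 87. If some genes do respond, the false share of the list runs from 19% to 94% over the scenarios examined. The documents do not say what share of genes to expect, so it cannot be claimed that most of the list will be false, only that the plan gives no means of knowing. The baseline point is a lesser one: validity is kept, but the contrast is undefined and power may be lost. The 950 follows directly from the gene count and the assumed level; the other sizes depend on the assumed effects, shares and correlations shown above.

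**What to change.** In section 13.5, exempt the whole-genome and oxylipin analyses from the no-adjustment sentence and add:

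> For these two analyses, Benjamini-Hochberg q-values, computed over all features tested in each, will be reported beside unadjusted p-values, with the number of features tested. A gene or metabolite will be described as identified only at a false discovery rate fixed before unblinding (e.g. 5% or 10%); all others will be labelled nominal. Each gene will be tested by ANCOVA of the week-12 value on study arm, with the participant's baseline value as covariate.

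The other secondary analyses can stay unadjusted. Moderated variance estimates and a sex covariate are optional.

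The cost is SAP wording and a few lines of standard code. No new samples are needed, because the primary endpoint already requires baseline nasal expression.

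The real price is fewer declared genes. With effects of 0.5 SD and 20 per arm, the list at q<0.05 may hold only about 0 to 17 true genes as the share changed goes from 1% to 20%. Baseline adjustment recovers part of the loss: at 1% changed by 1 SD and q<0.05, true genes rise from 24 to about 32, 56 or 126 at rho 0.3, 0.5 or 0.7. Because the unadjusted p-values are still shown, the full screen remains visible.
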